1 BACKGROUND

Population and literature review

Adults with learning disabilities are a key population within our hospitals (total estimated population 930,400: 2.16% of adults in England) (3). They require significantly more hospital care than the general population (4), with 1.9 times the expected number of episodes of admitted-patient care (5), 2.6 times the bed day rates of other patients (5) and have a longer than average length of stay (5,6) of between 3.7 (5) and 5.75 days (7). People with profound and multiple learning disabilities are significantly more likely to have an unscheduled emergency readmission than other people with learning disabilities (8).

In addition to their higher rates of admissions, people with learning disabilities experience poorer care in comparison to the general population within this setting. This has led to avoidable deaths during hospital admissions (9–15). During a hospital admission, people with learning disabilities experience higher levels of avoidable adverse events and poor safety outcomes compared to the general population (7,10,16) including poor quality of care and postoperative outcomes (16) and have a 2.7-fold higher incidence of experiencing five key avoidable hospital patient safety incidents - adverse drug reactions, hospital-acquired infections, pressure ulcers, postoperative pulmonary embolism, deep vein thrombosis, and postoperative sepsis (7).

When people with learning disabilities have communication difficulties, even if they are able to communicate with support or with a communication system, carers are typically expected to make decisions on their behalf (17) and a number of reviews have identified it is also common for people with mild learning disabilities to be ignored by healthcare staff (17,18), who instead communicate with their carers (18–20).

Despite commitments to learning disability care and the introduction of Learning Disability Liaison Nurses, ward staff often rely upon family carers and specialist nurses to 'prop up services', rather than adapting their care to meet the needs of people with learning disabilities. This includes staff misunderstanding the requirement to make reasonable adjustments (required under The Equality Act, 2010) (9,10,15,21–24) or expecting implementation to be carried out by specialist staff (13,15,22,24–27).

Care continues to be 'haphazard' at the ward level, even within the same hospital (22). Reviews have identified that the care experienced by people with learning disabilities during a hospital admission is highly variable and unsafe (18–20,25,27,30,37). An integrative review of the hospital experiences of people with learning disabilities (19) found that reasonable adjustments were not consistently provided, while another key review found many examples of care failures, and failures to make reasonable adjustments at ward level (37). In their NIHR mixed-methods study, Tuffrey-Wijne and team (22) found evidence of a range of serious care omissions, including problems with nutrition, hydration, and delays in care and treatment, which were not included in incident reports. They concluded that care quality was "haphazard" throughout hospitals, with poor practice found even when there was good hospital management support and policies to support care for people with learning disabilities (40). Although they identified pockets of good practice, this varied significantly by ward, suggesting that poor care is not inevitable for patients with learning disabilities and that good care is attainable under the right conditions - however, to date these conditions remain unclear.

Reviews conclude that detailed research is needed to provide the evidence required to understand this variation (1), how reasonable adjustments are implemented and evaluated in practice (2,3) and how care is organised, adapted, and delivered for people with learning disabilities at ward level during a hospital admission (1,4–6). This includes a need for research into the care of patients known to be at higher risk of poor healthcare experiences (patients with complex needs and people from Black, Asian and minority ethnic groups and people who communicate non-verbally) (6,7). Ethnographic research is required to explore what happens to individual patients (4,7), following them to examine the "issues faced... at each point along the hospital journey" (2). However our systematic search identified only one ethnographic study that observed the hospital care of children with learning disabilities (8,9) and one study utilising a small number of very brief observations of children and adults' care (5).

People with learning disabilities have also been under-represented in research about their care. Methods that exclude people with severe or profound learning disabilities (10–15) are common and can be poorly implemented with people with mild learning disabilities (16–18).

Brief description of the study

In response, this exploratory study will provide a detailed examination of the experiences of adults with learning disabilities and the organisation and delivery of their care during a hospital admission. Objectives are to:

- 1. Understand care experiences from the perspectives of adults with learning disabilities and family carers during a hospital admission, including people with complex needs and profound learning disabilities.
- 2. Examine how care is organised and delivered for adults with learning disabilities during a hospital admission including how ward teams understand and respond to their needs.
- 3. Use the findings to co-design guidance with people with learning disabilities, carers and ward staff to deliver initial strategies to improve support for people with learning disabilities at the ward level during hospital admissions.

Methods

We will carry out ethnographic research following 8 case studies of adults with learning disabilities and their carers and hospital staff supporting and caring for them across a hospital admission, which will provide the detailed understanding of how care is organised, adapted and delivered at ward level, including how reasonable adjustments are made. We will include people from minority ethnic groups and people with profound learning disabilities in our sample, broadening our understanding of the hospital experience for both groups and developing new methodological approaches to the inclusion of people with profound learning disabilities in hospital research.

We will carry out the research in two hospitals using ethnographic methods: observation, interviews and document analysis. We will use a toolbox of accessible interview supports and spend time with people with profound and multiple learning disabilities during a hospital admission to learn about, include and interpret their non-verbal communications with the support of their carers.

Finally, we will create and adapt co-design methods and a methods toolkit that supports the inclusion of people with a range of needs, including people who communicate non-verbally. This will draw on and develop existing and adapted co-production techniques, tailoring them to the specific needs of people within these groups and including augmentative and alternative communication (AAC).

pneumonia (78). The nature of these recent avoidable deaths bear striking similarities to the 2009 report into the deaths of six patients with learning disabilities (11) which also involved inadequate nutrition and monitoring in hospital. The majority of avoidable deaths of people with learning disabilities are due to treatable causes (by timely and effective health care interventions). In 2019, treatable causes accounted for 507 per 100,000 deaths in people with learning disabilities, compared with 80 per 100,000 in the general population (75) and a 2022 Care Quality Commission report concluded NHS hospital care for people with learning disabilities remains a 'critical patient safety issue' (24).

The poor care experienced by people with learning disabilities during hospital visits has been identified within the NHS since the National Patient Safety Agency's (NPSA) report on patient safety for people with learning disabilities in 2004 (31). Following Mencap's report, Death by Indifference, in 2006, and the resulting investigation into the deaths of people with learning disabilities (11) the independent inquiry into hospital care for people with learning disabilities Healthcare for All (in 2008) made a series of recommendations of which the following have been put into practice: adding reasonable adjustments to care to NHS core standards, the establishment of a Learning Disabilities Public Observatory, a Confidential Inquiry into the premature deaths of people with learning disabilities (completed in 2013) (9) and the tracking of the pathways of care of people with learning disabilities (partly: the Reasonable Adjustment Flag on the National Care Records Service was introduced last year) (79). Learning Disability Liaison Nurses were appointed in response to this inquiry and the NPSA report in the early 2010s (22,30) and the Learning Disabilities Mortality Review (LeDeR) programme was set up in June 2015 to review the deaths of people with learning disabilities. People with learning disabilities are a key group highlighted in the NHS Long Term Plan (80), which has committed to: reducing health inequalities for people with learning disabilities, taking action to prevent avoidable deaths, making reasonable adjustments to care, making sure "the whole NHS has an awareness of the needs of people with a learning disability" and improving the quality of inpatient care. National NHS learning disability improvement standards were introduced in 2018 (81) and are benchmarked each year by NHS Improvement. Relevant standards are: respecting and protecting rights (including making reasonable adjustments), inclusion and engagement of people with learning disabilities and their families and carers as partners in care, and workforce having the skills and capacity to meet the needs of people with learning disabilities. Mandatory training in learning disabilities and autism was introduced for healthcare workers recently under the Health and Care Act (2022).

3 THEORETICAL FRAMEWORK

Symbolic interactionism is the theoretical framework used for this study. This aims to provide an interpretive understanding of the social world, with an emphasis on interaction. We will use ethnography, which studies people's actions and accounts within their natural everyday settings and collect relatively 'unstructured' data from a range of sources (including observation, informal interviews and documentary evidence) (95). The aim is to explore the detail of often unnoticed everyday life, trying to read the tacitly known scripts and schemas that organise ordinary activities. The aim of our approach is to uncover original insights into the everyday ward care of people with learning disabilities (including people with profound learning disabilities) within the acute hospital setting and to understand how the wide range of social

actors within these settings (hospital staff) actively respond to these conditions through their actions. Ethnography allows us to examine these elements and the interplay between them. The value of this approach is the depth of understanding and original theory generation it can provide, including findings which are transferable more widely to other settings (96) that examine how context shapes and influences the quality, safety and delivery of care (97,98).

This research builds on work undertaken by this team to increase the inclusion of people with profound learning disabilities in research (62,84), NIHR ethnographies examining the hospital care of vulnerable populations (85–87), a systematic review of interventions to include people with learning disabilities and other cognitive impairments in care decisions (88), reasons for ward-level care omissions (89,90), and the difficulties in implementing individualised care at ward level (91). Our work to date has explored and theorised why nursing care for vulnerable people is more likely to be missed (91), and to explore and understand care omissions within the wider ward and hospital context, where difficult decisions are made to balance different kinds of care tasks (90), but which can reflect the underlying prioritisation of certain kinds of care for certain kinds of patients, and care rationing and allocation that can disadvantage certain groups and/or the time required to carry out personalised fundamental care (92–94).

4 RESEARCH QUESTION/AIM(S)

This exploratory ethnographic study will examine the experiences of adults with learning disabilities and the organisation and delivery of their care during a hospital admission.

4.1 Objectives

- Understand care experiences from the perspectives of adults with learning disabilities and family carers during a hospital admission, including adults with complex needs and profound learning disabilities.
- Examine how care is organised and delivered for adults with learning disabilities during a hospital admission including how ward teams understand and respond to their needs.
- Use the findings to co-design guidance with adults with learning disabilities, carers and ward staff to deliver initial strategies to improve support for adults with learning disabilities at the ward level during hospital admissions.

4.2 Outcome

The goal is to provide insights into an "intractable problem" – the need to improve hospital care for adults with learning disabilities. This study will provide insights into key areas of the organisation and delivery of care and the appropriate methodological approach to inform a programme of research that includes adults with severe and profound learning disabilities. The outputs described below would encourage change in clinical practice at site level, policy level, and through building greater inclusion of adults with learning disabilities (including profound learning disabilities) in research that will influence policy and practice in the future.

Outputs will be co-produced in collaboration with our PPI groups (adults with learning disabilities, carers) and in workshops with nursing staff from both hospitals.

For NHS hospitals we will deliver:

- Recommendations for the organisation and delivery of appropriately adapted care for adults with learning disabilities at ward level (shared with local sites, NHS England and national Mencap).
- A masterclass for ward staff in each site to promote care that supports the needs of adults with learning disabilities during a hospital admission, with a focus on the needs of adults with profound learning disabilities (this may include the recognition of deterioration, distress and pain in adults who communicate nonverbally). The feasibility, acceptability and initial evaluation of this training will be assessed to explore its implementation in future research.
- A briefing to NHS England and the Care Quality Commission to improve the monitoring and oversight of the care of adults with learning disabilities at ward level

To support the development of the next stages of this research programme and the wider research community (including current NIHR research (NIHR205211)) we will:

- Co-produce guidance in collaboration with adults with learning disabilities, and adults with complex needs and their carers on their inclusion in healthcare improvement research, which we will share with the research community and UKRI funding bodies
- Develop co-design methods and a methods toolkit that supports the inclusion of adults with a range of needs, including adults who communicate non-verbally.

We will also produce an academic paper on care experiences and ward organisation of care for adults with learning disabilities.

5 STUDY DESIGN and METHODS of DATA COLLECTION AND DATA ANALYIS

This project will use ethnography (with embedded case studies, observation, interviews, document analysis) to understand how care is experienced by adults with learning disabilities and how it is organised and delivered by ward teams during a hospital admission. JH will carry out all data collection and analysis with the support and mentoring of KF. As described below, PPI groups will also be involved in the analysis and interpretation of data.

In response to objective 1 we will recruit 8 case studies of adults with learning disabilities (4 per hospital) who are admitted within two large general hospitals in England over a four-month period and their carers and hospital staff supporting and caring for them.

For each case study, ethnographic in situ interviews with adults with learning disabilities and family carers will be carried out to explore their experiences of care during their hospital admission. We estimate carrying out a series of at least four ethnographic interviews with each person with a learning disability and/or their family carers during their admission (total n=>32 interviews) as well as spending time 'alongside' adults with profound and multiple learning disabilities observing and interpreting their non-verbal communication with the support of their carer(s).

Drawing on team expertise (JH) in supporting, interviewing, and observing the care of adults with learning disabilities (including adults with profound learning disabilities), and involving vulnerable populations in research during a hospital admission (KF), we will use tailored methods of augmentative and adaptive communication for each participant and accessible interview tools. These will be agreed in discussion with the person and (if appropriate) their carer. For adults who communicate nonverbally or with few words, JH will work with their carer to interpret how they express assent, dissent and a range of emotions.

For all participants including those with varying degrees of verbal communication we will build on existing good practice in the use of interviews with people with learning disabilities (22,42,54,59). Our toolbox of adapted and augmentative supports will include adaptations that have already been successfully used on hospital studies with people with learning disabilities:

- Talking Mats (www.talkingmats.com), "a facilitated conversation approach used to supplement interviews by moving graphic images around to make options more concrete" (22,54,59)
- Use of pictures to guide discussion (59)
- Pictures and stories about care experiences (following (40))
- Use of a sticker activity about interactions with staff using happy and sad faces (59)
- Use of symbols including Makaton to support questions about care (following (22))

For people with profound learning disabilities these methods will not be appropriate, however, with support people may be able to express preferences or emotional responses to the here and now (54) Building on the most innovative work to date with people with profound and multiple learning disabilities, JH will spend significant periods of time 'being with' (62) each individual during their hospital admission to understand the meaning of each participant's "personalised forms of action" and through negotiating and interpreting meaning with their carer (60) We will be guided by their carer(s)' advice on how best to spend time with and interact with the person (61) and how they express a range of emotions (fear, pain, boredom, frustration, contentment) (60). This will involve recording detailed 'micro-descriptions' of their body and facial movements, with interpretations discussed with their carer(s) during the admission (60,61,64)

This will produce detailed understandings of care experiences from the perspectives of adults with learning disabilities and family carers during a hospital admission, including people with complex needs and profound learning disabilities.

In response to objective 2,

At ward level, for each case study participant, we will observe (where possible) the routine bedside care they receive during their admission. Ethnographic observations will focus on:

- routine care at the bedside including: mealtimes and hydration; personal care (we will not observe intimate care); observations and medication rounds (including vital signs); to provide understandings of the routine organisation and delivery of care.
- staff attending the bedside and visits from specialists (including Learning Disability Liaison Nurses, medical teams, Speech and Language Therapists, and Physiotherapists) to examine interactional approaches during everyday care.
- nursing handovers, medical rounds, and MDTs (as they relate to the case studies) to examine decision making, involvement of the person and family, any adaptions, and discharge plans.

In addition:

-Ethnographic in situ short interviews with ward staff attending the bedside (approximately 8 per case study) and directly caring for participants to explore how they understand the participant's care and communication needs.

- -Documentary examination of hospital passport and medical records to examine care across the admission and how it is recorded.
- -Ward level documentation on staffing levels and patient acuity during the periods of observation to provide context.

The four-month period of data collection will deliver 160 hours of detailed ethnographic observations, across the two hospital sites. Observation periods will be carried out over three days/shifts a week across their admission, providing approximately 20 hours per case study. Observational fieldnotes and in situ short interviews will be taken during observation periods and written up into more detailed data on the same day (producing approximately 175,000 words of data). No identifiable data (individual names, ward names, hospital name) will be recorded during data collection. All notes will use pseudonyms for patients and carers, and staff role only will be used in notes.

This will produce new understandings of how care is organised, adapted, and delivered for adults with learning disabilities during a hospital admission including how ward teams understand and respond to their needs.

Analysis

Data sets will be transcribed by JH into anonymised word documents or collected using handwriting software on a tablet and converted into Word files. Data will be checked and cleaned in Word. All tablets are provided by University of Southampton and password protected. These word documents will be entered into NVivo for analysis. The goal of analysis will be to create a conceptual model of how care is organised, adapted, and delivered for people with learning disabilities during a hospital admission via: (1) a narrative approach to deliver a series (n=8) of detailed case studies (interviews, observation, document analysis) that illuminate individual trajectories during an admission. This will illustrate the experiences of a range of people with learning disabilities across different clinical contexts, experiences, and outcomes. These case studies will be used to inform theory development to support and extend the ethnographic analysis of everyday care. They will also be used to inform output development including anonymised case scenarios.

- (2) To analyse the ethnographic data (observation, in situ interviews, document analysis) an inductive process will be used, drawing on a grounded theory approach. To develop concepts and theories from the data we will develop initial 'sensitising concepts', using the constant comparative approach to deliver understandings about the provision of hospital care for people with learning disabilities that are transferable beyond local contexts (100)
- (3) The ethnographic and case study analyses will be examined, refined, and brought together during the process of co-production to develop strategies to support hospital care. We will use NVivo to manage data and analysis, enabling us to develop a wider conceptual analysis and detailed case studies that illuminate key concepts and theory development.

We will also use this study to provide an analysis of the practicality and acceptability of the research methods used (inclusive interview and observational approaches). Ethnography is appropriate to support this through detailed recording in-situ of the methodological approach in practice.

Participant details will remain confidential as per the requirements of the Data Protection Act (2018) and the University Hospital Southampton NHS Foundation Trust data management policy. Linked anonymity will be guaranteed (each participant will be allocated an ID on entry to the study and code and participant list will be stored separately). The code sheet that links codes with individual identifying

details will be stored on a password protected file on a password protected computer, and in a locked filing cabinet, separate to any research data storage. Any research data stored will be associated with individual codes not identifying details. All physical data will be stored in a locked cabinet at the University and all electronic data on a password protected file on a network drive that is accessible only through the research team members' password protected accounts. This will only be accessed by members of the research team. Files relating to the project may sometimes be stored on researchers' local laptop disks, which are protected by a university login. All sensitive files will be stored on the network drive where feasible, or if away from network access and access is critical, saved to the local laptop disk with a password known only to the research team. Before being shared in reports or published in articles, details of participants will be limited to ensure individuals cannot be identified and quotes will be attributed to pseudonyms.

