7.2.1 Size of sample

Our decision to recruit eight patients represents a feasible number to recruit and observe over a fourmonth period at both hospitals concurrently for the purposes of this exploratory study. The rationale for our sample size was based on the known populations of people living with learning disabilities in hospital, our discussions with learning disability liaison nurses working in hospital settings, and expert advice received during the NIHR peer review process during the submission of our grant application.

Our discussions with local learning disability liaison nurses have identified that they have an average admission rate of 20 people with a learning disability every month. This reflects the average admission rates identified in the literature (101). Using GP records and national statistics of hospital admissions, a screening study estimated that within an average-sized local health area approximately 5 adults with learning disabilities will be in hospital every day, each staying for an average of 3.7 days, or as long as 7.4 days in some departments, with significantly longer stays in medical and surgical specialties than members of the general population (102), but this was likely to be an underestimate due to low recording of people with learning disabilities on GP records compared to estimated prevalence in the population. People with severe and profound learning disabilities, a key group of interest in this study, are the most likely people with a learning disability to be identified by hospitals (5,22).

Using this data, extrapolated from the study above, even with longer stays of 7.4 days (30 days/7.4 days stay*5 people= 20) we estimate there will be 80 admissions within each hospital site over the 4 month period of data collection – 160 eligible patients in total – allowing for a cautious 5% recruitment rate.

In addition, we will also be recruiting carers and staff supporting and caring for these eight case study patients. We anticipate this will involve 16-24 carers and 64 members of hospital staff, creating a total sample size of 96.

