7.2.2 Sampling technique

Sampling in ethnography requires a flexible, pragmatic approach, using a range of variables that may influence the phenomena, and what is known based on the available literature. Probability sampling is not appropriate, instead non-probability sampling will generate analytically - rather than statistically - generalizable findings (103). The number of sites and participants are considered appropriate on the basis of the quality and appropriateness of the sample and when data saturation has been achieved, rather than on the basis of sample size (103).

We will initially use maximum variation sampling (104) to ensure we include people with learning disabilities who are under-represented in work exploring health inequalities, such as the LeDeR reports (75), and are more likely to have a poor experience of health services (17,23). Given the high representation of research with or through carers, we will also approach people with a range of carer support, including people who attend hospital without carers. However, as the study progresses, this approach will be refined to identify a purposive sample, to ensure our sampling reflects the patient population. Thus, sampling will include people with a learning disability who represent a range of factors that may influence care delivery, and where possible, socio-demographic factors:

- Severity of learning disability (mild to profound)
- Primary reason for the admission, including planned and unplanned admissions.
- People from Black, Asian and Minority Ethnic groups with a learning disability.

- · Expected length of stay
- To include people attending hospital with differing levels of support, who have a full-time family
 or professional carer, or no or limited support.

We will use translation services in NHS settings where required.

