As the study progresses, learning disability liaison nurses and ward managers will be asked to identify people in line with recruiting a range of people following the sampling criteria described in 7.2.2 (e.g. by ethnicity and by planned or unplanned admissions).

We will work with both hospitals concurrently to maximise recruitment opportunities with the support of staff (including collaborators).

In all cases of patient identification described above, the researcher will only be told which ward to visit for recruitment and will ask the ward manager to screen her current patient list for any adult with a learning disability. No identifying patient details will be shared with her. The researcher will always discuss the study with the ward manager or 'nurse in charge' on the relevant ward and seek initial verbal consent for her to be present on the ward to carry out observations of care should consent be gained from the patient and their carer. If the nurse in charge agrees, she will ask them to gain initial verbal consent from the patient and/or their carer (if supporting) for the researcher to approach the patient to discuss the study. If they provide consent for her to approach to discuss the study, she will discuss the project when a carer involved in their hospital support is present. If they are alone, she will ask if they would like a friend, carer or supporter to be there when she discusses the study and if so, she will return when that person is available.

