11.2 Appendix 2 - Schedule of Procedures (Example)

As described in section 7.3.1 we will be recruiting 8 case studies including patients, carers and staff and collecting data over a four month period in two hospitals. We are therefore unable to give an exact number of visits per week. In addition as this is an ethnographic study we will not be collecting baseline and follow-up data at specific times, but instead collecting data on 8 case studies using ethnographic methods. JH will make weekly visits to the nurses in charge of the medical and surgical wards (due to greater lengths of stay and numbers of people with learning disabilities in these specialisms (5)) and other wards identified as having higher admissions of people with learning disabilities on each site to screen their admissions through discussion with the ward leader (rather than directly through access to care records, which only the patient team can access). The PI (JH) will visit the hospital as often as required during this period to visit wards identified by learning disability nurses as having potentially eligible patients and their families and discuss the study with them. When somebody consents to participate in the study, JH will immediately begin ethnographic observations. Observation periods will be carried out over three days/shifts a week across their admission.

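### Does a 3.7-day average stay make the planned 20 hours of observation per case, 160 hours in all, unattainable?

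*Protocol*

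**What the plan says.** Section 5 (objective 2) gives a total, "The four-month period of data collection will deliver 160 hours of detailed ethnographic observations, across the two hospital sites", and a rate per case, "Observation periods will be carried out over three days/shifts a week across their admission, providing approximately 20 hours per case study". Appendix 2 repeats the frequency: "Observation periods will be carried out over three days/shifts a week across their admission". It adds that an exact number of visits per week cannot be given, and that observation starts at once when a person consents. Section 5 plans eight cases, four per hospital, and qualifies bedside observation as done where possible. The Study Summary confines fieldwork to the admission.

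On length of stay, Section 1 quotes 3.7 to 5.75 days, and Section 7.2.1 describes patients as "each staying for an average of 3.7 days, or as long as 7.4 days in some departments". Section 7.2.2 lists "Expected length of stay" among the factors to be varied in sampling. Section 7.1 sets no minimum stay. Neither Section 5 nor Appendix 2 gives hours per session or the stay behind the 20 h.

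**The concern.** The total is worded as a firm yield, but its ingredients are not all given. Taken as a rate, three sessions in seven days means fewer than two sessions in an average stay of 3.7 days, and 20 h would then need sessions of more than 12 h. The 7.4-day figure in Section 7.2.1 is the cautious case for recruitment, because longer stays mean fewer admissions, but the favourable case for observation. It is therefore natural to ask whether the shorter average was overlooked.

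If it was, the eight detailed case narratives would rest on much less material than described, and the short-stay cases would be the thinnest.

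**Working it through.** **Inputs from the Protocol.** Eight cases; about 20 h per case; 160 h in total; three sessions a week (Section 5, Appendix 2); stays of 3.7, 5.75 and 7.4 days (Sections 1 and 7.2.1).

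**Assumptions, not in the Protocol.** Hours per session h = 6.67, 7.5 or 12; delay from admission to consent of 0 or 1 day.

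**1. The stated total.** 8 × 20 = 160 h. It reproduces exactly.

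**2. Pro rata reading.** Sessions = (stay − delay) × 3/7; hours needed per session = 20 / sessions.

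- 3.7 days, no delay: 1.59 sessions, 12.6 h each; one-day delay: 1.16 sessions, 17.3 h each.
- 5.75 days: 2.46 sessions, 8.1 h each; with delay 2.04 and 9.8 h.
- 7.4 days: 3.17 sessions, 6.3 h each; with delay 2.74 and 7.3 h.

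Total over eight cases = 8 × sessions × h, shown as no delay / one-day delay:

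| h | 3.7 days | 5.75 days | 7.4 days |
|---|---|---|---|
| 6.67 | 85 / 62 h | 131 / 109 h | 169 / 146 h |
| 7.5 | 95 / 69 h | 148 / 122 h | 190 / 165 h |
| 12 | 152 / 111 h | 237 / 195 h | 304 / 263 h |

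The totals run from 62 to 304 h and lie on both sides of 160 h. The assumptions decide the direction.

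**3. Weekly-quota reading.** One week's quota is three sessions. 20 / 3 = 6.67 h per session gives 20 h, with no unusual session length. If sessions start 24 h apart, the time from the start of the first to the end of the third is 48 + h:

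- h = 6.67: 54.67 h = 2.28 days.
- h = 7.5: 55.5 h = 2.31 days, yielding 3 × 7.5 = 22.5 h.

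Both fit in 3.7 days. After a one-day delay 2.7 days remain, and both still fit: for example, consent at 10:00 with sessions that day and the next two. Counting only two whole days (2 × 7.5 = 15 h per case, 120 h in total) discards the remaining 0.7 day, which is long enough for a session. The delay that a 3.7-day stay can absorb is 3.7 − 2.28 = 1.42 days at 6.67 h, or 3.7 − 2.31 = 1.39 days at 7.5 h.

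**4. Where it does fall short.** With a two-day delay, 1.7 days (40.8 h) remain. Two sessions of 7.5 h need 24 + 7.5 = 31.5 h and fit; three do not. That case yields 15 h, or 13.3 h at 6.67 h per session. Losing one 6.67 h session takes 6.67 / 160 = 4.2% off the total.

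**The case for a change.** The best case for amending the text is that bunching sessions works only if observation starts early, and the Protocol itself makes some delay foreseeable. Screening covers people already in hospital, and the researcher's own ward rounds are weekly (Section 7.3.1). For a patient who is alone and wants a supporter, "she will return when that person is available". If a carer joins the study, another person must act as personal consultee (Section 7.3.2). Very long sessions are no escape: 175,000 words over eight cases is about 21,900 words each, and at 1.59 sessions that would mean roughly 13,800 words written up on the same day by one researcher. Length of stay is varied on purpose with no minimum, so a flat 20 h per case cannot be equally true of all.

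Part of this stands. Session length, assumed stay and start of observation are not stated, and hours will follow length of stay to some degree. But the liaison nurses are asked every weekday and also flag admissions planned for the same week, which can bring the delay close to zero. The ward visits go to medical and surgical wards because stays there are longer, and longer cases can offset shorter ones. The word-count argument tells against 12.6 h sessions, which the weekly-quota reading does not need.

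An explicit rule of observing every day in short stays would gain little. Three consecutive days are already allowed, so it adds at most a fourth day in a 3.7-day stay. The cost falls on participants who may be unwell and on a sole researcher covering two hospitals.

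**Conclusion.** No change is called for. The shortfall at 3.7 days depends on a pro rata reading that the text does not impose. Under the equally natural reading of up to three sessions within the week, 20 h per case is reached with sessions of about 6.7 h, even with one day lost before consent. This assumes consecutive-day sessions and an hour of consent that leaves room for a session on the same day. Cases with less than about 2.3 days left after consent would drop to roughly 13 to 15 h or below.

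That is missing detail on a planning figure which the Protocol already calls approximate and limits to what is possible. No estimate, precision statement or decision rule rests on 160 h; Section 7.2.2 judges adequacy by the quality of the sample and by saturation. Reporting the hours actually observed in each case, as an ethnographer would normally do, shows any unevenness.
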